## 6.13.3.6.3. Definitions of Participant ADA Status

Treatment-emergent (TE) ADA-evaluable participants: a participant with a non-missing baseline ADA result and at least 1 non-missing postbaseline ADA result.

TE ADA-unevaluable participant: any participant who does not meet the evaluable criteria.

Baseline ADA Present (preexisting antibody): ADA detected in a sample collected up to the first

dose date and time.

Baseline ADA Not Present: ADA is not detected, and the corresponding PK concentration is missing or below the drug tolerance limit in a sample collected up to the first dose date and time.

Treatment-emergent ADA positive (TE ADA+) participant: an evaluable participant who had a:

- baseline status of ADA Not Present and at least 1 postbaseline status of ADA Present with titer ≥2\*MRD, where the MRD is the minimum required dilution of the ADA assay.
- baseline and postbaseline status of ADA Present, with the postbaseline titer being 2 dilutions (4-fold) greater than the baseline titer. That is, the participant has baseline status of ADA Present, with titer 1:B, and at least 1 postbaseline status of ADA Present, with titer 1:P, with P/B ≥ 4.

As shown in Figure GPIA. 6.2 , a titer is expected when ADA assay result is Detected. On occasion, the corresponding assay cannot be performed, in which case a titer value will be imputed for the purpose of TE ADA determination. A baseline sample with detected ADA and no titer is imputed to be the minimum required dilution (MRD) (1:10) and a post-baseline sample with ADA detected and no titer is imputed to be one dilution above the MRD (1:20).

TE ADA Inconclusive participant: A TE ADA-evaluable participants TE ADA Inconclusive if  $\geq 20\%$  of the participant's postbaseline samples are ADA Inconclusive and all remaining postbaseline samples are ADA Not Present.

TE ADA negative (TE ADA-) participant: A TE ADA-evaluable participant is TE ADA- when the participant is not TE ADA+ and not TE ADA Inconclusive.

## 6.13.3.6.4. Analyses to be Performed

The count and proportion of participants who are TE ADA+ will be tabulated by treatment group, where proportion are relative to the number of participants who are TE ADA evaluable, as defined above. The tabulation will include the number and proportion of participants with ADA Present at baseline and the number and proportion of TE ADA+ participant exhibiting each type of cross-reactive antibodies.

This analysis will be performed for

- the planned treatment period
- the entire postbaseline period including follow-up.

A summary will be provided of the count and percentage of tirzepatide-treated participants experiencing specific TEAE (see Table GPIA.6.8) by participant TE ADA status (TE ADA+, TE ADA-, TE ADA Inconclusive) during the planned treatment period. The PT will be ordered by decreasing incidence in TE ADA+ status group.

TE AE category	Criteria	
Hypersensitivity reactions	actions Anaphylaxis SMQ (narrow or algorithm)	
	Hypersensitivity SMQ (narrow)	
	Angioedema SMQ (narrow)	
	Severe Cutaneous Adverse Reaction SMQ (narrow)	
Injection site reactions	Injection site reaction HLT	
	Infusion site reaction HLT	
	Administration site reaction HLT	

 Table GPIA.6.8.
 Adverse Events for Analysis with Immunogenicity Results

Abbreviations: HLT= high level term; MedDRA = Medical Dictionary for Regulatory Activity; SMQ = Standardised MedDRA Query; TEAE = treatment-emergent adverse event

Additional immunogenicity analyses as determined later may be presented. The relationship between antibody titers, the PK parameters, and pharmacodynamics (PD) response to tirzepatide may also be assessed.

Cases of TE ADA that are associated with TEAEs of either hypersensitivity or injection site reaction will be classified as AESIs.

### 6.13.3.7. Hypersensitivity Reactions

Two main analyses are performed in support of assessment of potential immediate hypersensitivity, including anaphylaxis as well as potential nonimmediate hypersensitivity.

**Time Period A**, of potential immediate hypersensitivity includes all TEAEs occurring from start of study drug administration up to 24 hours after end of study drug administration. For events without the hypersensitivity electronic case report form (eCRF), only date (no time) information is collected, the event occurred on the same date as the study drug injection date will be included in Time Period A.

**Time Period B**, of potential non-immediate hypersensitivity, includes all TEAEs occurring more than 24 hours after the end of study drug administration, but prior to subsequent drug administration.

The counts and percentages of participants who experienced a TEAE will be summarized by PT with decreasing frequency by treatment.

Detailed searching criteria can be found in Appendix 1. Within query, individual PTs that satisfied the queries will be summarized. For Time Period A analysis, the Anaphylactic reaction SMQ algorithm will be summarized. Also, a single event may satisfy multiple SMQs, in which case the event contributes to every applicable SMQ.

## 6.13.3.7.1. Hypersensitivity Reactions

The cases of treatment-emergent hypersensitivity will be considered as AESIs. All serious hypersensitivity events will be collected with the SAE form. A listing of participants with serious hypersensitivity reactions may be provided if deemed necessary.

## 6.13.3.8. Injection Site Reaction

Injection site reactions, incidence and rates, and related information reported via the "Injection Site Reactions" eCRF will be summarized by treatment. Information to be summarized includes the location of the reaction, timing of the reaction relative to study drug administration, and characteristics of the injection site reaction: erythema, induration, pain, pruritis, and edema.

Patient-based analysis and event-based analysis may be provided if necessary. The patient-based analysis summarizes all injection-site reaction (ISR) questionnaire forms for an individual patient with a single statistic, typically an extreme value. This analysis allows each patient to contribute only once for each parameter, at the expense of a focus on the most extreme events. By contrast, the event-based analysis summarizes all ISR questionnaire forms received, without regard to individual patients. This provides characteristics of ISR events as a proportion of all events for which questionnaire responses were provided, at the expense of some potential bias due to differential contribution of individual patients to the analysis.

The counts and percentages of participants with treatment emergent injection site reaction will be summarized by treatment using the MedDRA PTs. Detailed searching criteria can be found in Appendix 1.

The PT will be listed for summary in decreasing order of incidence for tirzepatide-treated participants.

### 6.13.3.8.1. Injection Site Reactions

The treatment-emergent injection site reactions (for example, abscess, cellulitis, erythema, hematomas/hemorrhage, exfoliation/necrosis, pain, subcutaneous nodules, swelling, induration, inflammation) will be considered as AESIs.

The counts and percentage of participants with treatment-emergent ISRs will be summarized by treatment. A listing of participants with treatment-emergent ISRs may be provided, if deemed necessary.

### 6.13.3.9. Major Adverse Cardiovascular Events

The following positively adjudicated major adverse cardiovascular events (MACE) will be considered as AESIs:

- o death due to cardiovascular AEs
- o myocardial infarction (MI),
- hospitalization for unstable angina,
- hospitalization for heart failure,
- coronary interventions (such as coronary artery bypass graft or percutaneous coronary intervention),
- cerebrovascular events, including cerebrovascular accident (stroke) and transient ischemic attack.

The counts and percentages of participants with positively adjudicated MACE may be summarized by treatment.

In addition, MACE reported by investigator may also be summarized although a major adverse

cardiovascular event reported by investigator is not considered as AESI.

A listing of participants reporting MACE events, either reported by investigator or identified by the clinical endpoint committee (CEC), may be provided.

### 6.13.3.10. Major Depressive Disorder/Suicidal Ideation

The treatment-emergent major depressive disorder/suicidal ideation or behavior will be captured as AESI. Adverse events will be searched using MedDRA PT terms. Detailed searching criteria can be found in Appendix 1.

The counts and percentages of participants with TEAEs will be summarized by treatment group using MedDRA PT nested within SMQ. Events will be ordered by decreasing frequency in the total tirzepatide group nested within SMQ. A listing of participants with major depressive disorder/suicidal ideation or behavior may be provided if deemed necessary.

Additionally, suicidal ideation and behavior, and depression will be assessed by the investigator via spontaneously reported AEs and through the use of the Columbia-Suicide Severity Rating Scale (C-SSRS) and the Patient Health Questionnaire (PHQ-9).

### 6.13.3.10.1. Patient Health Questionnaire

Total scores for the PHQ-9 range from 0 to 27 with total scores categorized as

- none (not depressed): 0 through 4
- mild: 5 through 9
- moderate: 10 through 14
- moderately severe: 15 through 19, and
- severe: 20 through 27.

Shift tables will be provided showing the counts and percentages of participants within each baseline category (maximum value) versus each postbaseline category (maximum value) by treatment.

Additionally, the following 3 outcomes of interest will be compared between treatments (based on the maximum value during baseline and postbaseline):

- any increase in depression category (ie, worsening of depression): includes participants in the none, mild, moderate, or moderately severe category during baseline and with at least 1 postbaseline measurement
- increase from No or Mild Depression to Moderate, Moderately Severe or Severe Depression: includes participants in the none or mild depression category during baseline and with at least 1 postbaseline measurement; and
- increase from Mild or Moderate Depression to Moderately Severe or Severe Depression: includes participants in the mild or moderate depression category during baseline and with at least 1 postbaseline measurement

Sensitivity analysis will be conducted using the Modified ITT - Safety Analysis Set excluded data completed by investigator.

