10.3.4.4.3. Depression, Suicidal Ideation, and Behavior

In addition to the summary of TEAEs, suicide-related events will be assessed by C-SSRS, and depression related symptoms will be assessed using PHQ-9.

Suicidal ideation, suicidal behavior, and self-injurious behavior without suicidal intent, based on the C-SSRS, will be listed by participant and visit.

The PHQ-9 total score will be summarized by treatment groups.

The analysis details will be provided in the SAP.

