## 6.2. General Considerations

Statistical analysis of this study will be the responsibility of Eli Lilly and Company (Lilly) or its designee. Some analyses and summaries described in this analysis plan may not be conducted if not warranted by data (e.g., few events to justify conducting an analysis). Additional analyses of the data may be conducted as deemed appropriate.

Unless otherwise noted, tests of treatment effects will be conducted at a 2-sided alpha level of 0.05, and the confidence interval (CI) will be calculated at 95% 2-sided.

Unless specified otherwise, efficacy and safety will be assessed using the modified intention-totreat (mITT) population, and data will be analyzed based on the randomized treatment (that is, not the actual treatment received by the participant). For primary efficacy analysis, the efficacy analysis will be conducted using Efficacy Analysis Set (EAS). Safety analysis will be conducted using Safety Analysis Set (SS).

Summary descriptive statistics for continuous measures will include sample size, mean, standard deviation (SD), median, minimum, and maximum. The analysis model to make comparisons among treatment groups relative to continuous measurements assessed over time will be either analysis of covariance (ANCOVA) or a mixed model for repeated measures (MMRM).

Kaplan-Meier method will be used for estimation of cumulative event-free survival rates over time, and Cox proportional hazards regression analysis will be used to compare hazards rates among treatments.

Summary statistics for categorical measures (including categorized continuous measures) will include sample size, frequency, and percentages. Logistic regression will be used to examine the treatment difference in binary efficacy outcomes if there is a need to adjust for covariate. Otherwise, Fisher's exact test will be used to examine the treatment difference.

Summary statistics for discrete count measures will include sample size, mean, SD, median, minimum, and maximum.

Unless specified otherwise, baseline will be defined as the last available non-missing measurement during Visit 1 to Visit 2. For the safety related parameters, the definition of baseline and postbaseline are specified in Table GPIA.6.2.

Analysis Set	Analysis Type	Baseline	Postbaseline
SS	1.1) Treatment-	The baseline period is defined	Starts after the first dose of study
	Emergent Adverse	as the start of screening and	treatment and ends at the end of the

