## 6.13. Safety Analyses

Unless specified otherwise, safety assessments will be based on the SS (Table GPIA.6.1). All events that occur between the first dose date of study drug and the end date of study participation will be included, regardless of the adherence to study drug.

The statistical assessment of homogeneity of the distribution of categorical safety responses between tirzepatide doses and placebo will be conducted using Fisher's exact test, unless specified otherwise.

For the selected continuous safety parameters, the mean change from baseline differences vs. placebo will be assessed via an MMRM using REML. Data from scheduled visits will be utilized for this analysis unless specified otherwise, the model for the analysis during 52 weeks treatment period will include sex, presence of comorbidities at randomization, treatment group, visit and treatment-by-visit interaction as fixed effects, and baseline value of the safety parameter as a covariate. To model the covariance structure within participants, the unstructured covariance matrix will be used. If this model fails to converge, the covariance structures specified in Section 6.12.1.1 will be tested in order until met convergence. If the data does not warrant the MMRM model, then ANCOVA model will be conducted.

For selected safety parameters, time-to-first-event analysis via the Cox-proportional hazards model may be conducted. Participants without the event will be censored at the end of study participation. For participants experiencing the event, the "time-to-first-event" will be the time (in days) from first dose to first occurrence of the event.

Where necessary, the rate of events will be analyzed using a generalized linear mixed-effects model assuming the number of events follow a negative binomial distribution and with treatment as a fixed effect. The logarithm of days during the active treatment period will be adjusted as an offset to account for possible unequal treatment duration of follow-up between participants.

Unless otherwise specified, all the analyses listed in this section will be conducted using SS in the postbaseline period: up to 52 weeks treatment period plus the safety follow-up (Visit 801, if applicable) for all randomized participants.

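### The SAP omits the PHQ-9 total-score summary stated in the protocol and compares arms only on worst-score categories, which are insensitive to small average shifts

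*SAP*

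**What the plan says.** Protocol 10.3.4.4.3 (Depression, Suicidal Ideation, and Behavior): "The PHQ-9 total score will be summarized by treatment groups". It then adds: "The analysis details will be provided in the SAP". This is a descriptive commitment; no between-arm test is named.

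SAP 6.13.3.10.1 (Patient Health Questionnaire) introduces the score with "Total scores for the PHQ-9 range from 0 to 27 with total scores categorized as", followed by five bands cut at 5, 10, 15 and 20. Two displays follow:

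- a shift table of "each baseline category (maximum value) versus each postbaseline category (maximum value) by treatment";
- three yes/no outcomes: any band increase; none or mild to moderate or worse; and mild or moderate to moderately severe or worse. Here "the following 3 outcomes of interest will be compared between treatments (based on the maximum value during baseline and postbaseline").

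SAP 6.13 (Safety Analyses) says the assessment of categorical safety responses "will be conducted using Fisher's exact test, unless specified otherwise". SAP 6.2 adds that "tests of treatment effects will be conducted at a 2-sided alpha level of 0.05". SAP 6.13 also provides a continuous route: "For the selected continuous safety parameters, the mean change from baseline differences vs. placebo will be assessed via an MMRM using REML". PHQ-9 is not named there.

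The Schedule of Activities places PHQ-9 at Visits 1 and 2, at weeks 12, 24, 36, 44 and 52, and at Visits 99, ED and 801. A completer therefore has two baseline and six post-baseline scores. Scores of 15 or more at Visit 1 or 2 are excluded (Protocol 6.2, criterion 18).

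**The concern.** The protocol states a summary that the SAP does not contain. Protocol 10.3.1 says that non-principal changes of method, with their justification, go into the SAP or the clinical study report; the SAP gives none here.

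PHQ-9 is also treated differently from comparable safety measures. The SAP specifies by-visit summaries for pancreatic enzymes, calcitonin, vital signs, ECGs and laboratory tests, and MMRMs for pancreatic enzymes, eGFR and UACR.

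Depression and suicidality form an adverse event of special interest. A general worsening of about one point would leave most participants inside the 0-4 or 5-9 band. At 70 per arm the planned comparisons would probably miss it, although the scores to show it are collected.

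**Working it through.** **1. The text.** The other SAP provisions that might supply the summary do not. Table GPIA.6.2 defines change from baseline for labs, vital signs and ECGs. Section 6.13 offers its MMRM for selected parameters without listing PHQ-9. Section 6.2 permits additional analyses but commits to none. The omission stands.

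**2. The documents' own power figure.** None is given for PHQ-9. For percent weight change they state more than 90% with 70 per arm, 25% dropout, difference 11, SD 11 and two-sided alpha 0.025. With n = 70 × 0.75 = 52.5 per arm, the standardized difference is (11/11)/√(2/52.5) = 5.12. Power is Φ(5.12 − 2.24) = 99.8%, which agrees. The same 70 per arm and 25% dropout are used below.

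**3. Why bands lose information.** For a normal score cut once with a proportion p above the cut, efficiency relative to the uncut score is φ(z)²/[p(1−p)].

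- p = 0.30: 0.348²/0.21 = 0.58
- p = 0.10: 0.1755²/0.09 = 0.34
- p = 0.05: 0.22
- p = 0.02: 0.12

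Rarer outcomes lose more. The third outcome is further limited to participants who were mild or moderate at baseline.

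**4. Simulated power.** 70 v 70, two-sided 0.05, Fisher's exact test on the three outcomes against ANCOVA of the total score adjusted for baseline. All PHQ-9 inputs are assumptions. Two data models were used:

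- *Model A*: baseline mean 2, 3 or 4 (between-person SD 2, 2.5, 3), over-dispersed counts, 25% monotone dropout throughout, 1,500 trials per setting.
- *Model B*: mean/SD 2/2.5, 3/3 or 4/4, between-visit correlation 0.5 to 0.7, 800 runs per setting. Only the week-52 analysis carries 25% missing data, so its other figures are best cases.

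Model A, uniform 1-point rise:

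| Baseline mean | Three planned outcomes | Total score, averaged over on-treatment visits | Gain over best planned |
|---|---|---|---|
| 2 | 38 / 25 / 9% | 83% | 45 points |
| 3 | 27 / 20 / 11% | 66% | 39 points |
| 4 | 16 / 15 / 11% | 49% | 33 points |

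The gain is 11 to 23 points for a 0.5-point rise and 32 to 45 points for 1.5.

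Model B:

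| Effect | Best planned outcome | Week-52 total score | Mean of post-baseline scores |
|---|---|---|---|
| 0.5 point in everyone | 7-10% | 15-36% | 32-73% |
| 1 point in everyone | 19-28% | 34-76% | 75-98% |
| 1.5 points in everyone | 42-62% | 65-98% | 98-100% |
| 2 points in everyone | 74-90% | 85-100% | about 100% |
| Sustained 8-10 points in 10-20% | 20-65% | 25-75% | 49-94% |
| One-visit 8-10 point spike in 20-30% | 26-97% | 7-19% | 17-57% |

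Null rejection rates were 1.0-4.3% (Fisher) and 4.7-5.1% (ANCOVA) in model A, and 1.6-5.3% in model B.

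**5. Unequal maxima.** The baseline maximum is over two scores and the post-baseline maximum over up to six. In model B with no treatment effect (mean 3, SD 3, correlation 0.6), 32% of each arm still shows a band increase. This background dilutes the contrast.

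**The case against.** Worst-value analysis is a reasonable safety choice. The SAP uses it for pancreatic enzymes, liver tests and vital signs, and the protocol's PHQ-9 rules concern individuals reaching 15 or more, which a maximum catches and a mean dilutes. Including Visit 801 follows the stated safety period. Depression is also covered by adverse-event searches, and suicidality by C-SSRS tables and listings. All of this stands, and it is why the category displays should stay.

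A reader might infer that the SAP has discarded most of the power to detect a depressive effect. The documents do not support that:

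- The missing item is descriptive. The protocol never planned a total-score test, so none was removed. The power argument concerns the absence of any total-score comparison.
- The loss depends on the pattern of effect. At 2 points the best planned outcome keeps 74-90% of the all-visit power. For a sustained large rise in a minority it keeps about 70-90% of the week-52 power. For a brief spike it is the stronger analysis.
- No PHQ-9 mean, SD, correlation or expected shift is documented. The two models also disagree on a week-52-only analysis: it gains 1 to 6 points in model A at a 1-point rise and clearly more in model B. How much is due to banding and how much to using a single value is therefore unsettled.

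Nor do the documents show a decision against the summary. It is absent by omission, and SAP 6.2 leaves room to add it. Room to add is not a commitment, however, and deferring details to the SAP does not make the summary itself optional.

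**Conclusion.** The point holds in a limited form. The SAP does not carry out the protocol's total-score summary, gives no reason, and compares arms only on categories of each participant's worst score. That part rests on the text alone.

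The planned comparisons fit large or brief individual worsening and are insensitive to small average shifts. Under the assumed inputs, a uniform 1-point rise gives the best of them 16-38% power across both models, against 49-98% for a baseline-adjusted total score averaged over visits. The lower end (49-83%, model A) is the cautious one because it carries dropout. These figures are for an ANCOVA of person means; the MMRM itself was not simulated. The advantage is confined to small-to-moderate uniform shifts and sustained rises, and should not be read as a general loss of power.

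This should be corrected. It is a supportive safety analysis and does not affect the primary conclusions.

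**What to change.** Keep the shift table and the three category outcomes as the worst-value safety display. Add to SAP 6.13.3.10.1:

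- PHQ-9 total score and change from baseline, summarized by treatment and nominal visit. This alone restores the protocol commitment.
- Each tirzepatide dose compared with placebo by the Section 6.13 MMRM (sex, presence of comorbidities, treatment, visit, treatment-by-visit, baseline total score) over weeks 12, 24, 36, 44 and 52, reporting the average and visit-wise differences with 95% CIs.
- The average labelled as treatment-period, not on-treatment, because the Safety Analysis Set includes data regardless of adherence.
- ED-visit scores assigned to the nearest scheduled PHQ-9 visit, so that participants who stop early are represented.
- Visit 801 summarized separately.

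The cost is SAP wording and one table from data already collected, with no new visits or participants. The downside is one more supportive safety comparison, unadjusted for multiplicity as SAP 6.5 already provides, of a skewed score. The visit-wise summaries should be read beside the model.
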